	Family Caregiver Activation in Transitions (FCAT) Tool	х	X	х	x			
Outcome Mediators	Patient Activation Measure (PAM)	X	Х	х	х			
Mediators	Self-Efficacy Scale	х	X	х	х			
	Surgery-Related Knowledge Tool	х	х	х	х			
	Sociodemographic and Health Status	х						
Exploratory	STS General Thoracic Surgery Data Collection Form				x			
	Exit Interview Discussion Guide				x			
	RN Debriefing Form	After each intervention session						
Process	Intervention Fidelity Checklist	1st five participants and every 10th session thereafter						

Family Caregivers:

Distress Thermometer (DT) – The DT is an efficient, low subject burden measure to evaluate psychological distress over the past week, based on a scale of 0 (no distress) to 10 (extremely distressed). According to the National Comprehensive Cancer Network (NCCN), psychological distress is defined as mixed anxiety and depression symptoms. ⁹⁸ A cut-off of 3/10 indicates a need for intervention, with acceptable sensitivity (94.1%) and specificity (71.2%) compared to

IRB 17238 02/02/2023

the Hospital Anxiety and Depression Scale (HADS).⁷¹ The DT has been validated in FCGs, with receiver operating characteristics (ROC) of 0.88 relative to the HADS.^{71, 99} It is also validated in lung cancer patients.⁷⁰

Montgomery Borgatta Caregiver Burden Scale (MBCBS) – This 14-item tool was designed to measure the impact of caregiving on three dimensions of burden: objective, subjective demand, and subjective stress. Internal consistency for the three dimensions ranges from .81 to .90. The ordinal scale ranges from 1-5 (a lot less to a lot more). The following cutoff scores are interpreted as high burden: 1) a score of 23 or > for objective burden, 2) a score of 15 or > for subjective demand, and 3) a score of 13.5 or > for subjective stress.

Preparedness for Caregiving Scale – This is an 8-item scale of the Family Care Inventory by Archbold and colleagues. ¹⁰¹ Items are scored from 0 to 4, with higher scores indicating better preparedness. A mean score is tabulated for all items. Internal consistency ranges from 0.88 to 0.93. ^{102, 103}

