FCG Activation in Transitions Tool (FCAT) – This 10-item survey was designed to assess FCG's level of engagement and preparedness to care for patients during care transitions. Psychometric assessment was conducted in two randomly equivalent waves of participants

IRB 17238 02/02/2023

(N=434), including FCGs of patients with cancer and/or chronic lung disease. The estimated person-separation reliability was 0.84. 111

Patient Activation Measure (PAM) – This measure assesses patient "activation", which uses a Guttman-like scale that reflects a patient's level of engagement and empowerment in their healthcare. ¹¹² Cronbach's alpha from our pilot study was 0.92.

Self-Efficacy Scale - This tool is a modified version of the Self-Efficacy Scale developed by Lorig and colleagues. ¹¹³ It contains 8 items that assesses FCG's and patient's perceived confidence in self-management. Items are rated on a 4-point Likert scale, and higher scores represent higher confidence. Cronbach's alpha from our pilot study was 0.89.

Surgery-Related Knowledge Tool - This tool was developed by the investigators to assess FCG and patient post-operative recovery knowledge. Each item addresses specific content within the MSM intervention to assess changes in knowledge. Scoring is based on the number of questions answered correctly.

Exploratory:

Society of Thoracic Surgeons General Thoracic Surgery Database Data Collection Form – This form will be used to record clinical and surgical characteristics. These include date of diagnosis, pre-operative risk factors, pre-operative treatments, pre-operative pulmonary function tests, date of surgery, type of surgical procedures, admission date and status, clinical staging, postoperative events/complications, discharge date and status, discharge disposition, pathological staging, and smoking cessation plans.

Exit Interview Discussion Guide – Qualitative data will be obtained through semi-structured interviews using a discussion guide. The guide contains a series of overarching questions, presented in an open-ended fashion. The questions are designed to solicit FCGs' and patients' experiences with participating in the intervention. FCGs and patients will be interviewed separately.

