
(Table 5). Standard deviations (SD) were estimated from previous data. For activation, an improvement of the mean by 8.0 points could be detected with 80% power. For self-efficacy, an improvement of 2.0 points could be detected

IRB 17238 Packet: 26 with 80% power. For knowledge, a difference of 5.0 points can be detected with 88% for 80 dyads per group.

Sample Size and Power Calculation for Social Determinants of Health and Spiritual Well Being – Sample size calculation is based on linear multiple regression method using

G*power (Version 3.1.9.4). This method tests the null hypothesis that the proportion of variance of the outcome explained by a set of predictors is zero (i.e., $R^2=0$), while the alternative hypothesis is $R^2>0$. Significance level is 0.05 and power is 0.8. 20% of attrition was considered in calculation.

Two parameters need to be specified for sample size calculation⁷⁴: effect size and number of predictors. The effect size is the ratio of proportion of variance explained by a set of predictors and error variance⁷⁴. Since there is no published data for correlation between our outcomes and predictors in the target population (lung cancer), and due to the exploratory nature of the analyses, the effect sizes are estimates only. To cover

Effect size Number of predictors 0.15 0.25 0.35 137 87 65 14 162 104 80 19 184 119 92

132

102

203

24

Table 2. Sample size considering 20% attrition

potential effect sizes that our data may reveal, we employed different levels of effect size defined by Cohen⁷⁵: small 0.15, medium 0.25, and large 0.35. The total number of predictors is 24 for FCG arm and 23 for patient arm. However, some predictors come from the same SDH domain, thus they would be highly correlated. To avoid multicollinearity in multiple regression model, some predictors may be removed from the final model. Therefore, we also used different number of predictors to calculate sample size (**Table 2**). Assuming the effect size 0.35 and 20% attrition, our target sample size will be 51 dyads (102 total participants) to detect deviation of R² from zero with 0.05 significance level and 80% power.

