We will use semi-structured interviews to examine dyadic experiences with the MSM Intervention. Qualitative data will be analyzed by the PIs using the conventional content analysis approach. This approach is used to describe a phenomenon where existing theory or research literature is limited. Data from the tape-recorded interviews will be transcribed and analyzed using HyperRESEARCHTM qualitative software. Transcripts will be imported allowing for the development of analytic categories, data coding, and review of coded data. All data will be read repeatedly to achieve immersion and obtain a sense of the whole. Then, data will be read word by word to derive codes. Codes will then be sorted into themes based on links and relationships. Separate investigators with experience in qualitative data analysis ([name] and [name]) will conduct a final validation review of the codes and themes to ensure consistency and clarity across all qualitative data. Data discordantly coded will be discussed for refinement and consensus purposes.

Geriatric Assessment (GA) data for both FCGs and patients will be analyzed descriptively. We will use descriptive statistics (mean [SD], median [range], percentage [95% confidence interval]) to summarize GA scores and domains. We will also describe the patterns of changes in GA over time for both FCGs and patients. Changes will be calculated as post-surgery scores minus pre-surgery scores. Exploratory logistic regression models (univariate and multivariate) will be fitted to study the correlation between GA and FCG/patient outcomes.

COVID-19 qualitative data will be analyzed using content analysis approaches as described under exploratory aim 2.

Social determinants of health (SDH) data will be scored according to guidelines descriptively summarized. We will use multiple linear regression to test associations between baseline outcomes and SDH predictors. Baseline scores of outcomes activation, burden preparedness, self-efficacy, QOL and distress will be summarized with descriptive statistics. Distributions of SDH predictors will be summarized. For each outcome, we will use bivariate regression to assess the effect of one predictor at a time. Stepwise multivariate analysis will be performed to select all significant predictors (p<0.05). In addition, multicollinearity issues will be examined by calculating correlation matrix for all predictors and by checking variance inflation factors.

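### The social-determinants sample size takes the 102 observations needed for one regression and splits them into 51 caregivers and 51 patients, which gives about 39% to 41% power for the full models, not 80%

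*Combined protocol and SAP*

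**What the plan says.** In section 13.1, the paragraph on sample size for SDH and spiritual well-being tests whether R² is zero in a linear multiple regression, with significance level 0.05 and power 0.8. It adds that "20% of attrition was considered in calculation". A small table (labelled Table 2, like the outcome-measures table in section 12.1.3) gives sample sizes for effect sizes 0.15, 0.25 and 0.35 and several predictor counts. The entry for 24 predictors at 0.35 is 102.

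On the predictors: "The total number of predictors is 24 for FCG arm and 23 for patient arm". Because predictors from one SDH domain may be collinear, "some predictors may be removed from the final model". The conclusion, at effect size 0.35 with 20% attrition, is that "our target sample size will be 51 dyads (102 total participants") will detect a departure of R² from zero with 80% power.

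The SDH analysis later in 13.1 reads: "We will use multiple linear regression to test associations between baseline outcomes and SDH predictors". It then names the outcomes: "Baseline scores of outcomes activation, burden preparedness, self-efficacy, QOL and distress will be summarized with descriptive statistics". It describes one-predictor regressions, stepwise selection at p<0.05 and collinearity checks.

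**The concern.** A sample size for a regression counts the observations that enter that regression. The table's 102 is such a count. Turning it into 51 dyads supplies 102 people, but a model fitted to caregivers or to patients has at most 51 observations.

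The plan has no sentence stating that SDH models are role-specific. The evidence for it is this:

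- Predictors are counted separately for caregivers (24) and patients (23).
- Burden and preparedness are measured in caregivers only (section 12.1.3, outcome-measures table). The burden scale is described so: "This 14-item tool was designed to measure the impact of caregiving on three dimensions of burden".
- Activation uses a caregiver tool (FCAT), which assesses the caregiver's "level of engagement and preparedness to care for patients during care transitions", and a different instrument for patients (PAM). Quality of life uses COH-QOL-Family for caregivers and FACT-L for patients.
- No pooled SDH model is described, nor any adjustment for correlation within a dyad.

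Only distress and self-efficacy use one instrument in both roles. For burden and preparedness pooling is impossible whatever was intended.

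What is at stake is the reading of the sub-study. With an 80% power claim on record, a full model that shows no significant R² could be taken as evidence of no association, when the test had about a 40% chance of finding the assumed effect.

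**Working it through.** **Inputs (section 13.1).** Test of R² = 0 in linear multiple regression; α = 0.05; target power 0.80; f² = 0.35, which is R² = 0.35/1.35 = 0.26; p = 24 (caregivers) or 23 (patients); 20% attrition; 51 dyads.

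**Formula.** Power = P(F′ > F crit), where F′ is noncentral F with df1 = p, df2 = n − p − 1 and noncentrality λ = f²·n, and F crit is the 95th percentile of the central F with the same degrees of freedom.

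**Step 1: reproduce the plan's figure.** For p = 24 and f² = 0.35, n = 84 gives 79.9% and n = 85 gives 80.7% (df2 = 60, λ = 29.75). So 85 are needed, and 85 × 1.2 = 102. The same rule, n × 1.2 rounded up, reproduces all 12 printed cells:

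| p | n for 80% at f² 0.15 / 0.25 / 0.35 | n × 1.2, rounded up (as printed) |
|---|---|---|
| 9 | 114 / 72 / 54 | 137 / 87 / 65 |
| 14 | 135 / 86 / 66 | 162 / 104 / 80 |
| 19 | 153 / 99 / 76 | 184 / 119 / 92 |
| 24 | 169 / 110 / 85 | 203 / 132 / 102 |

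The label of the first row is not legible in the text available; p = 9 fits it. The table is therefore internally consistent, and 102 is the requirement for one regression.

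**Step 2: power with 51 observations.** At f² = 0.35, λ = 0.35 × 51 = 17.85.

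| Predictors | df2 | Power at n = 51 |
|---|---|---|
| 24 (caregivers, all) | 26 | 39.1% |
| 23 (patients, all) | 27 | 41.2% |
| 19 | 31 | 49.9% |
| 14 | 36 | 62.6% |
| 9 | 41 | 76.8% |
| 8 | 42 | 79.8% |
| 7 | 43 | 82.7% |

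Seven or fewer predictors are needed for 80%. The smallest entry in the plan's own table, 65, already exceeds 51.

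**Step 3: effect detectable with 80% power at n = 51, all predictors.** Caregivers: f² = 0.758, so R² = 0.758/1.758 = 0.43. Patients: f² = 0.724, so R² = 0.724/1.724 = 0.42. The planned value is f² = 0.35 (R² = 0.26), which the plan already labels large.

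**Step 4: attrition.** Step 2 grants all 51 per role, because the SDH questionnaire and the modelled outcomes are baseline measures. If 20% were lost, 51 × 0.8 ≈ 41 would remain, and power would be 24.4% (24 predictors) and 26.1% (23).

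Separately, an allowance for 20% loss divides by 0.8: 85/0.8 = 106.25, so 107. Multiplying by 1.2 leaves 102 × 0.8 = 81.6, about 82, which gives 78% for a single sample. That slip is small beside the split.

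**Step 5: what each role needs with all predictors.** Caregivers 85, patients 83 (p = 23: n = 82 gives 79.7%, n = 83 gives 80.5%). With × 1.2 these become 102 and 100; with division by 0.8, 107 and 104.

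**The case against.** The strongest reply is that role-specific models are an inference. The plan claims 80% power for 51 dyads, not for a 51-person model. Elsewhere section 13.1 lists PAM and FCAT together as one activation outcome (Table 5) and pools caregiver and patient data for Exploratory Aim 1. The spiritual well-being paragraph refers to research questions that this protocol does not set out, so a fuller specification may exist elsewhere. A pooled sample of 102 with no attrition would have about 91% power with 24 predictors, ignoring dyad correlation. It stands that the plan should say which it means. But pooling cannot apply to burden or preparedness, and neither the SDH analysis nor its sample size deals with correlated pairs.

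Second, predictors may be dropped, so 39% to 41% is the least favourable case. That is fair: across the tabulated counts the range is 39% to 77%. Yet no tabulated count reaches 80%, and the target was itself taken from the 24-predictor cell. The figure for seven predictors also assumes that the reduced set is fixed without reference to the outcome and still carries f² = 0.35; stepwise selection at p<0.05 guarantees neither.

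Third, the analysis section describes screening and stepwise selection, with no decision resting on a full-model R², and the plan calls the work exploratory with effect sizes that are estimates only. This limits the consequence. It does not make the stated power correct.

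Fourth, 51 dyads is a target and not a cap, since the study calendar schedules the questionnaire for both roles at baseline and earlier enrollees may be invited. More could be achieved, but the 80% claim is tied to 51. Non-response among retrospective invitees would lower power further.

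**Conclusion.** The concern holds. The plan's table is right; the step from the table to the target is wrong, because the requirement for one regression was spread over two roles. At the plan's own f² of 0.35 and α of 0.05, with 51 analysed per role, power is about 39% for the full caregiver model and 41% for the full patient model, against a stated 80%.

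This assumes that the models are fitted by role. For burden and preparedness that is certain; for the other outcomes it is strongly indicated but not written. It also assumes no loss from the 51. The sub-study is exploratory, and the main trial's size and aims are untouched.

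**What to change.** Restate the paragraph per role, by one of two routes.

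1. **Keep 51 dyads.** State about 39% power (caregivers, 24 predictors) and 41% (patients, 23 predictors) at f² = 0.35, and 80% only for a model limited to seven or fewer predictors. The cost is a less favourable stated figure.
2. **Raise the survey target.** Aim for at least 85 analysed caregivers and 83 analysed patients: about 102 dyads with the plan's × 1.2 allowance, or 107 if 20% loss is really expected. That is 85 − 51 = 34 more analysed caregivers and 83 − 51 = 32 more analysed patients. Both targets lie within the 200 dyads, so the trial's enrolment target need not rise, provided enough dyads are still to enrol or can be re-contacted. The documents give neither accrual to date nor a response rate. Section 5.6 allows earlier enrollees to be invited, but only English speakers and with addendum consent.

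Under either route, state whether SDH models are role-specific. If distress or self-efficacy is to be pooled across roles, say so and say how within-dyad correlation is handled. If an attrition allowance is kept, divide by 0.8.

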2.2 Overview of Proposed Study

This prospective, longitudinal, mixed-methods RCT is designed to test the efficacy of the MSM Intervention in lung cancer surgery. In Aims 1, 2, and 3, outcomes and mediators will be examined across 3 time points (discharge, 1 and 3 months post-discharge) by treatment group using baseline as covariates We will also test intervention effects on FCG cancer support services use and patient healthcare resource use. The primary outcome is the change in scores from baseline to discharge (immediate effect) and 3 months post-discharge (sustained effect). In EA 1, we will explore moderators and reciprocal relationships. In EA 2, we will qualitatively explore participants' experience with the MSM Intervention.

This study will be conducted in compliance with the protocol, Good Clinical Practice (GCP) and the applicable regulatory requirements.

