Data management is of key importance in this study. Our institutional research informatics core will develop an electronic data entry, capture, and storage system that will perform tracking functions (accrual, enrollment, consenting, data collection, and intervention delivery). We will develop a query system to address data validity and integrity by making early identification of cases of recruitment irregularity, data collection inconsistency, data inaccuracy or incompleteness. Data will be audited for accuracy prior to scoring and analysis.

Our primary data analysis will be according to intention-to-treat, i.e. all participants will be included in the analysis whether or not they received all prescribed intervention components. Participants who are lost to follow-up due to mortality will not be included. Reasons for study dropout will be recorded. Participants with missing items will be compared with those having non-missing items to determine whether missing data are random or can be accounted for by other variables. Broadly, our data may be missing at random (MAR) or missing not at random (MNAR). Generalized linear model with robust (sandwich) variance estimator model will be fitted to the data, with time, baseline, treatment arms, and interaction of time and treatment as explanatory variables. This approach provides valid standard errors with repeated measurement of individuals. It also accommodates missing time points by using the model of time effects to reduce bias. For MNAR, a pattern mixture model⁵⁵ will be fitted to the data to correct for informative drop-out. In particular, three patterns will be defined: a pattern consisting of participants who died during the study period, a pattern of participants with relapse, and a pattern of participants who remained disease free. Within each pattern, data will be modeled by the random effects model. To compare treatment arms, the effects of both arms will be respectively estimated using a weighted average across all patterns weighted by their sample proportions.

IRB 17238 02/02/2023

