These two hypotheses will be tested in the same way. We will address the effect of the intervention on FCG psychological distress, burden, preparedness for caregiving, and QOL at months 1 and 3, adjusted for baseline response. Scores for all outcome measures will initially be summarized graphically and numerically at baseline, month 1, and month 3, for each stratum, along with simple diagnostic plots. The need for transformation will be accessed. A generalized linear mixed model will be fit to estimate the distribution of 1 month and 3 month score as a function of treatment, stratum, occasion (month 1 or 3) and baseline value. The robust (sandwich) variance estimator will be used to accommodate the correlation of the two occasions, and the estimated treatment effect for the adjusted average of the 1 and 3 month outcomes will be estimated and tested, in order to limit multiplicity with respect to occasions, and to improve upon the designed power by combining information, effectively reducing standard deviations relative to those used for planning. This is similar to the analysis of average outcome for the two post-treatment occasions, except that it accommodates missing outcome evaluations by attributing observations to the appropriate occasion (comparing like with like), and avoids overstating information. Analysis of average outcome does provide a convenient robustness check. Each analysis will be a repeated measures ANCOVA statistical design, removing variances prior to examining mean squares for the group by occasion interactions, and covarying the baseline scores. The independent variable will be group (intervention vs. attention control). Hypothesis 1.3: The intervention group will have higher social work referrals and family resource center use.

FCG cancer support services will be evaluated by recording social work referrals and family resource center use. Each subject will be classified as having an event or not. There is no baseline value, but the data will be tabulated by surgery stratum, and tested for homogeneity (interaction) before estimating and testing the overall treatment effect.

IRB 17238 02/02/2023

Specific Aim 2: Test the effects of the MSM Intervention on patient outcomes and healthcare resource use at discharge and 3-months post-discharge, comparing intervention and attention control groups.

Hypothesis 2.1: The intervention group will experience lower psychological distress and higher OOL.

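### The analysis called intention-to-treat excludes deaths, and its pattern mixture model has no pattern for living drop-outs and none defined for caregivers

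*Combined protocol and SAP*

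**What the plan says.** The key text is the missing-data paragraph of section 13.1.

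- It defines the primary analysis as intention-to-treat: "all participants will be included in the analysis whether or not they received all prescribed intervention components". The next sentence is "Participants who are lost to follow-up due to mortality will not be included".
- It adds "Reasons for study dropout will be recorded", and "Participants with missing items will be compared with those having non-missing items" to see whether other variables explain the missingness.
- If data are MNAR, a pattern mixture model is to correct for informative drop-out. Its three patterns are "participants who died during the study period, a pattern of participants with relapse, and a pattern of participants who remained disease free". The arms are then compared "using a weighted average across all patterns weighted by their sample proportions".

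Other sections bear on this:

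- E.5, Specific Aim 1, fits a mixed model "to estimate the distribution of 1 month and 3 month score as a function of treatment", stratum, occasion and baseline. Aim 2 uses the same plan for patient scores.
- Section 2.2 defines the primary outcome as change "in scores from baseline to discharge (immediate effect) and 3 months post-discharge (sustained effect)".
- Hypothesis 2.2 is binary: each patient either had in-home nursing, an urgent care or ER visit, or a readmission, or did not.
- Section 5.3 gives the participant's own wish to stop as the sole ground for disenrollment.
- Section 13.1 plans for 200 dyads enrolled and 160 retained at 3 months.

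**The concern.** There are two faults in one paragraph.

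**Deaths.** Scores after death do not exist, so some rule for deaths is needed. The sentence removes the participant, however, and not just the undefined scores. Data already observed would be discarded because of something that happened after randomisation, which is not intention-to-treat. The rule also does not fit the died pattern a few lines later. If that pattern applies only to the MNAR analysis, the primary analysis omits deaths while the MNAR analysis averages over them. A gap between the two results could not then be read as the effect of informative drop-out.

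**Living drop-outs.** The model is meant to deal with informative drop-out, but no pattern is defined by drop-out. Someone alive who withdraws is grouped, by disease status, with people who completed. If withdrawal is informative beyond disease status and differs between arms, the planned model would not show it. Caregivers are the Aim 1 population and have no stated relapse status, so the patterns cannot be applied to them as written.

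**Working it through.** **1. The plan's own figure.** 200 × (1 − 0.20) = 160 dyads retained. This agrees with section 13.1 and leaves 40 lost.

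**2. Reach of the death rule.** Section 2.1 gives background mortality after lung cancer surgery: 6% in hospital, and twice that number in the six months after discharge. These are not trial rates. Timing within the six months is not given, so a constant rate is assumed.

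| Quantity | Calculation | Result |
|---|---|---|
| In-hospital deaths | 0.06 × 200 | 12 |
| Deaths within 6 months of discharge | 0.12 × 200 | 24 |
| Discharge to month 1 | 24 × 1/6 | 4 |
| Month 1 to month 3 | 24 × 2/6 | 8 |
| Discharge to month 3 | 4 + 8 | 12 |

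- *Month 1 scores.* Only patients who die between months 1 and 3 have an observed month 1 score to lose. That is about 8, assuming all of them answered at month 1. The range is 0 (no post-discharge deaths in that window) to 24 (all of them in it). In-hospital deaths lose no post-discharge score.
- *Hypothesis 2.2.* Every randomised patient can be classified, including those who die in hospital. Classifications lost: 12 + 12 = 24, range 12 + 0 = 12 to 12 + 24 = 36.
- *Discharge scores.* These are not counted, because the E.5 model uses months 1 and 3 only. If discharge is also analysed, as section 2.2 implies, discharge scores of patients who die later would be lost too.

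**3. Living drop-outs.** The plan does not say whether deaths fall inside the 40 planned losses. If outside, all 40 are living drop-outs. If inside, 40 − 24 = 16 remain, with a range of 40 − 36 = 4 to 40 − 12 = 28.

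**4. What the disease-status patterns can correct.** Suppose that, within a disease-status pattern, living drop-outs have true scores s points from those of comparable completers. The pattern mean is estimated from observed scores and misses this shift. If drop-out is unrelated to disease status, the error left in the treatment difference is s times the between-arm difference in drop-out.

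An illustration on assumed inputs uses the planned FACT-L difference of 101.3 − 93.7 = 7.6, drop-outs 10 points worse, and drop-out of 15% in the intervention arm against 5% in control. The difference over all randomised patients is 7.6 − 10 × (0.15 − 0.05) = 6.6. A simulation on these inputs (SD 17, 100 per arm, 5% relapse) gave 6.6 for all randomised patients, 7.6 for the missing-at-random model and 7.6 for the relapse/disease-free patterns. With 10% drop-out in each arm, all three were 7.6. This shows the mechanism only; it does not forecast the trial.

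**The case against.** Several counter-arguments have force.

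- *The sentence may mean only that nothing is modelled after death.* The plan uses available occasions elsewhere, the died pattern needs decedents' data, and Hypothesis 2.2 speaks of classifying each subject. This reading is possible. But the sentence excludes participants, not occasions, and two analysts could build different datasets from it.
- *Disease-course patterns are a legitimate MNAR assumption.* They are, and no single model covers every form of informative drop-out. Still, section 5.3 makes withdrawal the only disenrollment route, and reasons for drop-out are recorded without being used to define the patterns. Comparing participants with and without missing items describes missingness; it does not adjust for it.
- *A living drop-out pattern is not identified by itself.* This is correct. These participants have no month 3 score, so relabelling the patterns is not enough; a delta or another restriction is required.
- *Nothing suggests that an educational intervention affects mortality.* This is fair, and it limits the likely effect on the treatment difference.

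A reader might infer that caregivers of patients who die are dropped from Aim 1. The documents point the other way: the synopsis counts 400 individual participants, and section 5.3 ties disenrollment to the participant's own wish. A reader might also infer that relapse is not collected. It is not named among the listed data items, but those lists may not be exhaustive.

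**Conclusion.** The point stands as a low-grade should-fix. As written, the population is not intention-to-treat, the death rule and the died pattern are not reconciled, and the MNAR model neither separates living drop-outs nor says how caregivers enter it.

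The reach is about 8 of 200 patients losing an observed month 1 score (range 0 to 24) and about 24 losing a Hypothesis 2.2 classification (range 12 to 36). These counts rest on background mortality applying to this trial, and the central values also on a constant death rate after discharge. Between 4 and 40 living drop-outs would be pooled with completers, depending on how deaths are counted.

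It is tempting to conclude that the results will be biased, or biased towards the intervention. The documents do not support that. They give no drop-out or death rates by arm and no outcome difference for those who leave, so neither size nor direction can be derived. If deaths and drop-out are alike in both arms, the bias may be near zero.

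**What to change.** Amend section 13.1 and E.5 as follows.

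1. Delete the mortality exclusion. Analyse every randomised participant in the assigned arm, with all data observed up to death or withdrawal.
2. State the estimand for deaths, for example scores while alive, and check that the fitted model matches it. Use the same death rule in the primary and MNAR analyses, and do not average post-death scores into the estimate.
3. For Hypothesis 2.2, classify all randomised patients on events observed before death. Add a sensitivity analysis that counts death as an event, since an early death otherwise looks like low use. Report deaths by arm.
4. Confirm in one sentence that caregivers of patients who died stay in Aim 1.
5. Replace or supplement the disease-status patterns with a sensitivity analysis for living drop-outs, run separately for caregivers and patients, that shifts their unobserved scores by a stated range of deltas. The delta, or another stated identifying restriction, is required.

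The cost is SAP wording and slightly more analysis, repeated over about 12 quantitative outcomes (4 caregiver + 2 patient + 3 mediators × 2 populations). No new data collection is needed: drop-out reasons are already recorded, and resource use at the study centre comes from the chart audit. One limit remains. Use outside the centre is self-reported at 1 and 3 months and may be incomplete for patients who die.
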